## BACKGROUND

### *Study Purpose and Rationale*

Obstetrical hemorrhage is a leading cause of maternal morbidity and mortality worldwide with a significantly higher frequency and severity following cesarean delivery. In 2020, 31.9 percent of pregnant women in the United States underwent cesarean delivery, [1] making it the second most common operation performed. Though multiple complications can occur following cesarean delivery, hemorrhage morbidities are among the most common with significant cardiovascular implications [2]. Twin gestations are at particularly higher risk for postpartum hemorrhage due to impaired myometrial contractility and atony following overdistention; increased maternal blood volume; and increased uterine blood flow compared to singletons, yet the management of obstetrical bleeding following twin delivery remains identical to singleton delivery [3]. Current strategies to address intrapartum hemorrhage have relied on pharmacological and mechanical treatments after intraoperative identification. However, there is extensive work on prophylactic therapies administered intraoperatively to prevent obstetrical hemorrhage [4-6]. Recent evidence has emerged about the utility of prophylactic Methylergonovine for the prevention of obstetrical hemorrhage [7-8]. Methylergonovine, a semisynthetic ergot alkaloid, acts primarily on alphaadrenergic receptors of uterine and vascular smooth muscle, increasing uterine tone and promoting vasoconstriction. Masse et al [8] in a randomized trial of 80 women undergoing intrapartum cesarean delivery found that fewer patients who were allocated to the methylergonovine group received additional uterotonic agents (20% vs 55%, relative risk [RR] 0.4, 95% CI 0.2–0.6). Participants receiving methylergonovine were more likely to have satisfactory uterine tone (80% vs 41%, RR 1.9, 95% CI 1.5–2.6), lower incidence of postpartum hemorrhage (35% vs 59%, RR 0.6, 95% CI 0.4–0.9), lower mean quantitative blood loss (967 mL vs 1,315 mL; mean difference 348, 95% CI 124–572), and a lower frequency of blood transfusion (5% vs 23%, RR 0.2, 95% CI 0.1–0.6). Investigators concluded that the administration of prophylactic methylergonovine in addition to oxytocin in patients undergoing intrapartum cesarean birth reduces the need for additional uterotonic agents. Similarly, Senturk et al [7], in a prospective study of 1210 participants found that intraoperative, prophylactic methylergonovine decreased post-operative blood loss with no adverse side effects. Randomized trials of Methylergonovine as prophylaxis to prevent hemorrhage in cesarean

delivery have exclude twin gestations [7-8]. Currently, there remains a paucity of research regarding prophylactic procedures for twin cesarean delivery. Similarly, the use of Hemabate (carboprost tromethamine) is an effective uterotonic to reduce obstetrical hemorrhage. Hemabate, a prostaglandin F2 alpha agonist, similarly treats uterine atony by stimulating smooth muscle contraction. Unlike Methylergonovine, hemabate does not cause secondary vascular constriction and can be used in patients with blood pressure disorders. In a study of prophylactic Hemabate, Balki and colleagues assigned participants to receive either oxytocin 5 units intravenous alone, or with ergonovine 0.25 mg intravenous or carboprost 0.25 mg intramuscular immediately after delivery and found a reduction in postpartum hemorrhage. There is an opportunity to prophylactically address hemorrhage in high risk groups. Therefore, we propose a prospective randomized controlled trial which will compare maternal blood loss associated with prophylactic uterotonic treatment during cesarean delivery among patients with twin pregnancies. We hypothesize that prophylactic uterotonic therapy in cesarean delivery is associated with decreased maternal blood loss compared to standard care.

## RESEARCH AIMS & ABSTRACTS

*Research Question(s)/Hypothesis(es):* To evaluate whether prophylactic uterotonic therapy reduces maternal blood loss among individuals with twin gestations undergoing cesarean delivery.

*Primary Research Question:* Is the administration of prophylactic uterotonic therapy at the time of scheduled cesarean delivery after cord clamping of the second twin associated with decreased maternal blood loss among patients with twin pregnancies (based on primary outcome of maternal hemoglobin drop from preop to postoperative day #1)?

*Hypothesis:* Prophylactic uterotonic therapy in cesarean delivery among patients with twin pregnancies is associated with decreased maternal blood loss compared to placebo.

### *Scientific Abstract*

This is a randomized controlled trial of patients undergoing scheduled (daytime) cesarean section among patients with twin gestations. We propose a prospective randomized controlled trial which will compare maternal blood loss associated with prophylactic uterotonic therapy

during cesarean delivery among patients with twin pregnancies. We hypothesize that prophylactic uterotonic therapy in cesarean delivery is associated with decreased maternal blood loss compared to standard care. The target patient population for this study is women with twin pregnancies undergoing scheduled cesarean delivery. Subjects will be expected to do the following once they agree to participate: 1) Sign the informed consent 2) Enroll - randomized in preop to prophylactic methylergonovine or placebo.

## STUDY DESIGN

We propose a prospective randomized controlled trial which will compare maternal blood loss associated with prophylactic uterotonic therapy during cesarean delivery among patients with twin pregnancies. We hypothesize that prophylactic methylergonovine 200mcg IM or Hemabate carboprost tromethamine (250mcg/mL, 1mL syringe) in cesarean delivery is associated with decreased maternal blood loss compared to placebo. This is a randomized controlled trial of patients undergoing scheduled (daytime) cesarean section among patients with twin gestations. For our primary research question, we will compare the change in maternal hemoglobin from pre-op to postoperative day #1.

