### *Study Procedures*

Consented subjects who remain eligible for study participation on the day of their scheduled cesarean delivery will be randomized 1:1 by trained research personnel to one of two groups: Intervention group (Prophylactic methylergonovine 200mcg IM) or Control group (placebo same volume). If a blood pressure disorder of pregnancy is diagnosed, study participants will be randomized to one of two groups: Intervention group (Prophylactic carboprost tromethamine 250mcg IM) or Control group (placebo same volume). Randomization will occur on labor and delivery while the subject is in the preoperative area prior to delivery. The subjects will be taken to the operating room where anesthesia will be administered and cesarean delivery will be performed in routine fashion until delivery of the fetuses. Obstetricians, anesthesiologists, intraoperative research staff, and subjects will be blinded to study arm allocation. A trained member of the research team will perform randomization prior to delivery. Upon delivery of the second twin neonate, the anesthesiologist will administer the study drug;

subjects will receive either prophylactic methylergonovine 200mcg IM or saline placebo (identical volume) IM.

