If patients are not candidates to receive methylergonovine due to a blood pressure disorder of pregnancy (gestational hypertension, chronic hypertension, preeclampsia with or without severe features), they will be randomized to Prophylactic carboprost tromethamine 250mcg IM or Control group/placebo same volume Oxytocin will be administered (by the anesthesia team) in routine fashion immediately upon delivery. The remainder of the cesarean will proceed in routine fashion per surgical team. Uterotonics/blood transfusion may be administered per routine care as judged necessary by the surgical team. Blood loss at completion of the surgery will be estimated by the obstetric, nursing, and anesthesia teams with a final estimated blood loss (EBL) agreed on by all providers and recorded in the routine fashion in the medical record. Similarly, the quantitative blood loss (QBL) will be calculated and recorded. All mothers will receive routine postoperative and postpartum care. This includes administration of intravenous fluids (125 cc/h lactated ringers) until tolerating oral fluids. On postoperative day 1, maternal hemoglobin level will be assessed on a complete blood count per standard clinical care. Neonates will receive routine care. Race and ethnicity will be self-reported at the time of hospital registration and extraction from the medical record (fixed categories) to consider the generalizability of the results. All other data will be abstracted by the research team by review of both the maternal and neonatal medical records. All medical records will be reviewed through 30 days after delivery to identify any postpartum or postnatal complications.

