## STATISTICAL ANALYSIS

Based on the following parameters, the sample size was calculated for the primary outcome of mean hemoglobin change from pre-op to post-op day 1 between placebo and treatment groups. The analysis was conducted in Stata 17. From the protocol: Based on a prior study of cesarean deliveries in twin gestations [9], a mean (SD) change in hemoglobin level for elective cesarean delivery of 1.40 (0.83) g/dL was estimated. Up to 20% crossover rate from the treatment group to the placebo group will be assumed. Because there is no accepted definition of a minimum clinically important difference in postoperative hemoglobin change, effect size was based on the published SD of the mean. Given the burden of maternal morbidity and mortality due to postpartum hemorrhage, the investigators decided that even a 1-SD greater drop in postoperative maternal hemoglobin level with Methylergonovine treatment arm might alter clinical decision-making. Hence the parameters are as follows:

Effect size / difference in means: 0.83SD: 0.83 (assumed to be the same for both groups)

Allocation ratio: 1:1

Crossover rate: 20%

Power: 0.90

Alpha: 0.05 (two-tailed)

Assumed dropout rate: 10%

The sample size is 33 per group, or 66 total on the more conservative end, including adjustment for potential loss to follow up.

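### The primary hemoglobin-change comparison has no pre-specified adjustment for pre-op hemoglobin or randomisation stream, although both are known for every analysed woman

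*Combined protocol and SAP*

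**What the plan says.** Study Design gives the primary comparison in one sentence: "For our primary research question, we will compare the change in maternal hemoglobin from pre-op to postoperative day #1". Statistical Analysis states that "the sample size was calculated for the primary outcome of mean hemoglobin change from pre-op to post-op day 1 between placebo and treatment groups", and then lists the parameters, among them "Effect size / difference in means: 0.83SD: 0.83 (assumed to be the same for both groups" and "Allocation ratio: 1:1". The section contains nothing else on analysis: no test, model, covariate or stratified method. Its only adjustment is of the sample size, for loss to follow-up. An unadjusted comparison of mean change is the natural reading, but it is not stated.

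Study Procedures describes two randomisations. The first is methylergonovine against placebo. For the second, "If a blood pressure disorder of pregnancy is diagnosed, study participants will be randomized to one of two groups", namely carboprost or placebo. Both are done in the preoperative area, so stream is fixed before treatment. The day-1 value comes from routine care: "On postoperative day 1, maternal hemoglobin level will be assessed on a complete blood count per standard clinical care". The plan does not say how the two streams are combined. The Study Design hypothesis names both drugs against placebo, and there is one sample size of 66, so a single pooled treatment-versus-placebo comparison is the best-supported reading.

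**The concern.** The trial will hold two baseline variables for every woman in the primary analysis and plans to use neither as a covariate. With 1:1 allocation, a linear model that includes them estimates the same treatment difference, is at least as precise in large samples, and removes the effect of chance imbalance in baseline hemoglobin or stream mix. With about 30 women per arm, some imbalance is to be expected.

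The streams differ in both drug and population. A stream term makes the analysis follow the way the women were randomised.

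The second issue is the open choice. With no model fixed, both an adjusted and an unadjusted estimate can be produced and one preferred once the results are known.

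**Working it through.** **Inputs from Statistical Analysis.** Difference 0.83 g/dL; SD of change 0.83 g/dL; crossover up to 20%; power 0.90; two-sided alpha 0.05; dropout 10%; 33 per group.

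**The plan's figure.** Dilution by 20% crossover gives 0.83 × 0.8 = 0.664 g/dL, or d = 0.664/0.83 = 0.8. Then n = 2(1.960 + 1.282)²/0.8² = 32.8, so 33 per group (34 with the t distribution). This is before dropout: 33/0.9 = 36.7, so 37. Other routes also reach 33 with dropout included, for example 23/(1 − 0.20 − 0.10) = 32.9, where 23 is the undiluted t-based size. The plan does not show which was used. All are unadjusted two-sample calculations.

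**Unadjusted power.** Evaluable women: 33 × 0.9 = 29.7, taken as 30 per arm. With d = 0.8 and 58 df, t-based power is 0.861 (normal approximation 0.873). With no dilution (d = 1.0) it is 0.968.

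**Adjusted power.** The documents do not give the SDs of pre-op and day-1 hemoglobin (s1, s2), so they are assumed, with the SD of change held at 0.83:

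- correlation: ρ = (s1² + s2² − 0.83²)/(2·s1·s2)
- residual variance ratio: s2²(1 − ρ²)/0.83²
- cost of two covariates: 56 df, and variance multiplied by 1 + 2/55.

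For s1 = s2 = 0.9, ρ = (1.62 − 0.689)/1.62 = 0.575, and the ratio is 0.81 × (1 − 0.330)/0.689 = 0.787.

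| Assumed s1 / s2 (g/dL) | Variance ratio | Power, d = 0.8 |
|---|---|---|
| Unadjusted | 1 | 0.861 |
| 0.9 / 0.9 | 0.787 | 0.921 |
| 1.1 / 1.1 | 0.858 | 0.898 |
| 1.3 / 1.3 | 0.898 | 0.884 |
| 1.5 / 1.5 | 0.923 | 0.875 |
| 1.1 / 1.2 | 0.937 | 0.871 |
| 1.1 / 1.3 | 0.987 | 0.853 |
| 1.3 / 1.5 | 0.996 | 0.850 |
| 0.9 / 1.2 | 0.998 | 0.849 |
| 1.3 / 1.1 | 0.707 | 0.945 |
| Two covariates, neither prognostic | 1 | 0.849 |

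Break-even is at about 3.6% of the change variance explained. At d = 1.0, adjusted power is 0.988 (0.9/0.9), 0.973 (1.5/1.5) and 0.963 (0.9/1.2), against 0.968 unadjusted. Simulation (20,000 runs per case, assumed 25% in the carboprost stream, stream not prognostic) agrees: 0.918, 0.895 and 0.877 adjusted for equal SDs of 0.9, 1.1 and 1.5, against 0.857 to 0.864 unadjusted. Both estimators centre on 0.664.

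**Stream alone.** With an assumed share p = 0.2 in the carboprost stream and a difference of D SDs in mean change between streams, R² = v/(1 + v), where v = p(1 − p)D². D = 0.5 gives v = 0.04 and R² = 0.04. D = 1 gives v = 0.16 and R² = 0.14.

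**Size of a baseline imbalance.** The slope of change on baseline is ρ·s2/s1 − 1, which is −0.43 to −0.15 in the equal-SD cases. An imbalance of one standard error, s1√(2/30), moves the unadjusted estimate by 0.06 to 0.10 g/dL. The standard error of the unadjusted difference is 0.83√(2/30) = 0.214.

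**The open choice.** Under no treatment effect at 30 per arm (40,000 simulated runs per case; equal SDs of 0.9, 1.1 and 1.5; 25% in the carboprost stream), each analysis alone holds about 5% type I error. Reporting whichever p-value is smaller gives 7.2%, 6.7% and 6.4%. This is a worst case, not a prediction of conduct.

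**The case against.** The strongest reply is that the root gap is the absence of any named primary analysis. One sentence committing to an unadjusted comparison would close the selection problem, and preferring a covariate model is then a matter of efficiency. This is right about selection. It does not remove the reason to choose the more efficient model when the sentence is written.

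The gain is also not established by the documents. Every pre-op and day-1 SD is assumed, three of the nine pairs lose about 1 point of power, and at the undiluted effect unadjusted power is already 0.97. This stands, and the gain should be presented as a range. The risk is nevertheless lopsided: about 1 point lost at worst, against 6 to 8 points gained in the favourable cases.

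The stream term has little shown benefit in precision. At R² = 0.04, power with two covariates is 0.863 against 0.861 unadjusted. This stands too. The case for stream rests on matching the analysis to the randomisation. Likewise, a shift of 0.06 to 0.10 g/dL from baseline imbalance is modest beside a design difference of 0.83, or 0.664 diluted; it is 0.01 to 0.05 where the day-1 SD is larger.

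Finally, one treatment term commits the trial to a single effect for two drugs, and no section says how the streams are combined. The proposed model keeps the estimand that the hypothesis and single sample size imply; it does not introduce pooling. The plan should still state the pooling openly.

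**Conclusion.** The concern holds, as a change that should be made. The plan describes and sizes the primary analysis as a two-group comparison of mean change and fixes no model, while both covariates are already in hand. The unadjusted estimate is not biased. At 30 evaluable women per arm and d = 0.8, power moves from 0.86 to 0.88–0.92 for equal SDs of 0.9 to 1.5 g/dL, falls to 0.85 in the least favourable cases, and reaches 0.94–0.95 if the day-1 SD is smaller (1.3/1.1). These figures rest on the assumed SDs, full 20% dilution and the stated 10% dropout. The benefit of fixing the model in advance does not depend on those SDs.

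**What to change.** Add to Statistical Analysis, before any unblinded data are seen: *The primary analysis is a linear model of hemoglobin change on treatment group, with pre-op hemoglobin (continuous) and randomisation stream (methylergonovine/placebo or carboprost/placebo) as covariates; the adjusted mean difference with its 95% CI is the primary estimate.* Keep the unadjusted difference as a sensitivity analysis.

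Code stream as the randomisation actually used. Study Procedures ties the carboprost stream to blood pressure disorders alone, whereas the exclusion criteria send women with any methylergonovine exclusion to assessment for carboprost; the two sections must be reconciled. State also which pre-op hemoglobin measurement serves as baseline, since its timing is not defined.

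The cost is one sentence for the model, these two clarifications, and two degrees of freedom (58 to 56 at 30 per arm). At worst about 1 point of power is lost if neither covariate is prognostic. No new data are needed. Do not reduce the sample size or the dropout allowance in expectation of a gain.

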### *Study Procedures*

Consented subjects who remain eligible for study participation on the day of their scheduled cesarean delivery will be randomized 1:1 by trained research personnel to one of two groups: Intervention group (Prophylactic methylergonovine 200mcg IM) or Control group (placebo same volume). If a blood pressure disorder of pregnancy is diagnosed, study participants will be randomized to one of two groups: Intervention group (Prophylactic carboprost tromethamine 250mcg IM) or Control group (placebo same volume). Randomization will occur on labor and delivery while the subject is in the preoperative area prior to delivery. The subjects will be taken to the operating room where anesthesia will be administered and cesarean delivery will be performed in routine fashion until delivery of the fetuses. Obstetricians, anesthesiologists, intraoperative research staff, and subjects will be blinded to study arm allocation. A trained member of the research team will perform randomization prior to delivery. Upon delivery of the second twin neonate, the anesthesiologist will administer the study drug;

subjects will receive either prophylactic methylergonovine 200mcg IM or saline placebo (identical volume) IM.

If patients are not candidates to receive methylergonovine due to a blood pressure disorder of pregnancy (gestational hypertension, chronic hypertension, preeclampsia with or without severe features), they will be randomized to Prophylactic carboprost tromethamine 250mcg IM or Control group/placebo same volume Oxytocin will be administered (by the anesthesia team) in routine fashion immediately upon delivery. The remainder of the cesarean will proceed in routine fashion per surgical team. Uterotonics/blood transfusion may be administered per routine care as judged necessary by the surgical team. Blood loss at completion of the surgery will be estimated by the obstetric, nursing, and anesthesia teams with a final estimated blood loss (EBL) agreed on by all providers and recorded in the routine fashion in the medical record. Similarly, the quantitative blood loss (QBL) will be calculated and recorded. All mothers will receive routine postoperative and postpartum care. This includes administration of intravenous fluids (125 cc/h lactated ringers) until tolerating oral fluids. On postoperative day 1, maternal hemoglobin level will be assessed on a complete blood count per standard clinical care. Neonates will receive routine care. Race and ethnicity will be self-reported at the time of hospital registration and extraction from the medical record (fixed categories) to consider the generalizability of the results. All other data will be abstracted by the research team by review of both the maternal and neonatal medical records. All medical records will be reviewed through 30 days after delivery to identify any postpartum or postnatal complications.

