#### Exclusion criteria for methylergonovine:

- Subjects with known hypertensive disease: history of chronic hypertension, gestational hypertension or preeclampsia with or without severe features
- Use of protease inhibitors given known vasoconstrictive side effects with concomitant methylergonovine administration

- Hypersensitivity to methylergonovine or any of the ingredients

If patients meet any of the exclusions above, they will be assessed for the use of Hemabate and excluded if:

- Subjects with known asthma disease
- Hypersensitivity to Hemabate or any of the ingredients

Additionally, if subjects meet any of the following criteria, they will be excluded from participation:

- Participating in another intervention study where the primary outcome includes postpartum bleeding or thromboembolism, or the study intervention directly affects postpartum bleeding or thromboembolism
- Receipt of uterotonics, other than oxytocin, or planned or expected use of uterotonic prophylaxis
- Non-elective cesarean delivery

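### Women are randomised within two separate placebo comparisons, but the one planned treatment-versus-placebo contrast has no term for the comparison a woman entered

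*Combined protocol and SAP*

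**What the plan says.** Study Procedures randomises eligible women 1:1 to methylergonovine or placebo. It then adds a second randomisation, to carboprost or placebo: "If a blood pressure disorder of pregnancy is diagnosed, study participants will be randomized to one of two groups". The same section repeats the rule: "If patients are not candidates to receive methylergonovine due to a blood pressure disorder of pregnancy". The document never uses the word stratified, but two separate randomisations split by a baseline condition amount to two strata.

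The eligibility text under Exclusion criteria for methylergonovine words the carboprost route more widely: "If patients meet any of the exclusions above, they will be assessed for the use of Hemabate". Those exclusions cover hypertensive disease, hypersensitivity, and also "Use of protease inhibitors given known vasoconstrictive side effects with concomitant methylergonovine administration".

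The Research Aims (question and hypothesis) and the opening of Study Design ask about either drug against placebo. Statistical Analysis sizes one contrast, "mean hemoglobin change from pre-op to post-op day 1 between placebo and treatment groups", with one effect size, one SD, "Allocation ratio: 1:1" and this total: "The sample size is 33 per group, or 66 total". It names Stata 17 but no test, model, covariate or stratum term. Methylergonovine is the only drug named in three places: the enrolment step of the Scientific Abstract, the sentence on giving the study drug after delivery of the second twin, and the effect-size rationale ("with Methylergonovine treatment arm might alter clinical decision-making").

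**The concern.** A woman's blood pressure status fixes which comparison she joins, and it may also be related to her haemoglobin drop. If mean drops differ between the two comparisons, an analysis that ignores them leaves that variation in the error term. Power and confidence-interval width then suffer for no benefit, because the factor is known before randomisation.

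The pooled result is also an average over two drugs. Because Statistical Analysis does not say that the contrast is pooled and names only methylergonovine in its rationale, a reader could attach the planned power, or the conclusion, to methylergonovine alone. The sample size does not support that.

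**Working it through.** **Inputs from Statistical Analysis.** Difference 0.83 g/dL, SD 0.83 g/dL, 20% crossover, 10% dropout, power 0.90, two-sided alpha 0.05, 33 per group.

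**Assumptions not in the documents.** Share f of women in the carboprost comparison: 0.2 to 0.4. Difference Δ in mean drop between comparisons: 0.3, 0.5 or 0.8 g/dL, the last an extreme.

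**The plan's own figure.** The diluted effect is 0.83 × 0.8 = 0.664. Then n = 2(1.960 + 1.282)² × 0.83²/0.664² = 21.01/0.64 = 32.84, so 33 per group. This matches the stated 33 before any dropout; dividing by 0.9 gives 37. That mismatch is a separate matter. Since the plan says 33 already allows for loss, I use 33 × 0.9 ≈ 30 evaluable per arm.

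**Cost of the term when it is not needed.** By noncentral t, power at 33 per arm is 0.893 without the term and 0.892 with it; at 30 per arm it is 0.861 either way.

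**Case A: 0.83 is the within-comparison SD.** Under simple randomisation the unadjusted variance is 0.83² + f(1−f)Δ². Example, f = 0.4 and Δ = 0.8: 0.6889 + 0.24 × 0.64 = 0.8425, SD 0.918. The noncentrality is 0.664/(0.918 × √(2/30)) = 2.80, and power is 0.79. With the term it is 0.664/(0.83 × √(2/30)) = 3.10, and power is 0.86. Simulation (60,000 trials per cell, 30 per arm, f = 0.2/0.3/0.4) gives:

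| Δ (g/dL) | No term, simple randomisation | No term, comparisons balanced across arms |
|---|---|---|
| 0.3 | 0.855 / 0.852 / 0.852 | 0.856 / 0.853 / 0.854 |
| 0.5 | 0.842 / 0.835 / 0.829 | 0.848 / 0.846 / 0.844 |
| 0.8 | 0.813 / 0.795 / 0.789 | 0.824 / 0.817 / 0.807 |

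With treatment and comparison in the model, power is 0.854 to 0.865 and type I error 0.048 to 0.052 in every cell. Without the term, type I error is 0.048 to 0.051 under simple randomisation and 0.030 to 0.047 (conservative) when balanced.

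**Case B: 0.83 is the overall SD.** The unadjusted test keeps power of about 0.86. The within-comparison SD is now smaller: for f = 0.4 and Δ = 0.8 it is √(0.6889 − 0.1536) = 0.732, and power with the term is 0.93. Over the whole grid the adjusted power is about 0.86 to 0.93.

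**What each drug's own estimate can show.** The 95% half-width is t × 0.83 × √(2/n), with n per arm.
- Pooled, n = 30: 2.002 × 0.83 × 0.258 = 0.43 g/dL.
- Methylergonovine, n = 24/21/18: 0.48/0.52/0.56 g/dL.
- Carboprost, n = 6/9/12: 1.07/0.83/0.70 g/dL.

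Power for an effect of 0.664 within methylergonovine alone is 0.77/0.72/0.65, and within carboprost alone 0.24/0.36/0.47. The stated 0.90 can therefore only be meant for the pooled contrast.

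**The case against.** The case against giving this weight is strong, and much of it stands. An unadjusted comparison of randomised arms is valid. Its type I error is at or below nominal, and its loss of power is under one point at Δ = 0.3 and one to three points at 0.5. Even that loss depends on reading 0.83 as a within-comparison SD. The plan takes it from a prior study and applies it to whole treatment groups; on that reading there is no shortfall, and the term is purely a gain. The share and Δ come from outside the documents. The either-drug question is already stated in the Research Aims and Study Design, so the methylergonovine-only phrases look like leftover wording. The wider carboprost route in the eligibility text is incomplete cross-reference rather than contradiction, since Study Procedures does not say that blood pressure is the only route.

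Two stronger readings are tempting.
- A reader might infer that pooling biases the result. That would need allocation ratios that differ between comparisons. The ratio is not restated for carboprost, but the overall 1:1 in Statistical Analysis is consistent with 1:1 in both.
- A reader might infer that the trial is badly underpowered because the drugs may differ. If carboprost had half the effect, pooled power would be 0.67 to 0.78; with no effect, 0.43 to 0.68. Those figures already include the comparison term, so its absence does not cause them. Nothing in the documents says that the effects differ, and the Background calls carboprost effective. They limit interpretation and do not make this omission more serious.

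What remains is that no primary model is named, and a known design factor is left out of the one planned contrast.

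**Conclusion.** The point holds as an inexpensive improvement to the analysis, not as a threat to validity. Leaving out the comparison term costs from under one point of power to about seven, the latter only at an assumed 0.8 g/dL difference with 0.83 taken as the within-comparison SD. If 0.83 is the overall SD, nothing is lost against the plan, and the term raises power from about 0.86 to at most 0.93. In no scenario examined does including it do materially worse. All these figures rest on an assumed 20 to 40% carboprost share and 30 evaluable women per arm.

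The stated power and the primary conclusion belong to the either-drug strategy. The documents do not support a claim that the pooled test is biased, or a claim of low power from differing drug effects. The drug wording and the routing of women to carboprost are editorial matters to settle alongside.

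**What to change.** In Statistical Analysis, define the primary analysis as either prophylactic uterotonic versus placebo on haemoglobin change, fitted by a linear model with treatment and randomised comparison (methylergonovine or carboprost) as stratum. Report each drug's effect with its 95% CI as descriptive only. State that the power and the primary conclusion refer to the either-drug strategy; the stratum main effect does not deal with any difference between the drugs' effects.

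Accompanying edits:
- Reconcile the methylergonovine-only wording (Scientific Abstract enrolment step, drug-administration sentence in Study Procedures, effect-size rationale) with the Research Aims and Study Design.
- State the allocation ratio for the carboprost comparison.
- Reconcile the eligibility text with Study Procedures on who enters that comparison, so that the stratum is defined for every woman.

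The cost is a change of wording and one degree of freedom. The covariate is fixed at randomisation, so no extra patients or data are needed.

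### Does timing the study drug by the second twin's delivery in one place and by cord clamping in another change what the trial tests?

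*Combined protocol and SAP*

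**What the plan says.** Two sentences in the combined protocol and SAP say when the study drug is given.

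- Research Aims & Abstracts, primary research question: the prophylactic uterotonic is given "at the time of scheduled cesarean delivery after cord clamping of the second twin".
- Study Design, Study Procedures: "Upon delivery of the second twin neonate, the anesthesiologist will administer the study drug". The clause that completes this instruction is "subjects will receive either prophylactic methylergonovine 200mcg IM or saline placebo (identical volume) IM".

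For women with a blood pressure disorder of pregnancy, Study Procedures adds that "they will be randomized to Prophylactic carboprost tromethamine 250mcg IM or Control group/placebo same volume". It gives that stratum no separate time of administration. Background oxytocin has its own sentence: "Oxytocin will be administered (by the anesthesia team) in routine fashion immediately upon delivery".

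Clamping of the cord is mentioned only in the primary research question. The hypothesis that follows it and the opening of Study Design state no timing.

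**The concern.** The research question defines what the trial sets out to test, and Study Procedures is what the anesthesiologist acts on. If the first requires the cord to be clamped and the second does not, staff following the procedure to the letter could inject between delivery and clamping. That is earlier than the research question allows.

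Three things would then be at stake. The trial might deliver something slightly different from the intervention in its own question. The second twin might still be attached when a uterotonic is given. Operators might time the dose differently, which could make the treatment effect more variable. The instruction applies to everyone who is dosed, so the point looks broad even though its size is unknown.

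**Working it through.** No figure in the plan rests on the timing of the dose. The check therefore compares the texts and then asks whether anything statistical depends on the difference.

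**Step 1: the statements side by side.**

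- Primary research question: study drug, second twin, after clamping.
- Study Procedures, administration sentence: study drug, second twin, at delivery, cord not mentioned.
- Study Procedures, carboprost stratum: product and comparator stated, no time of its own. The general term for the study drug in the administration sentence can be read to cover it.
- Study Procedures, oxytocin: routine background care for everyone, not the study drug.

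Only the first two time the study drug. They agree on the drug, the twin and the operative step. They differ on whether clamping is named.

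**Step 2: can one dose satisfy both?** Let D be the time of delivery of the second twin and C the time its cord is clamped, with D before C. The research question requires a dose after C. The procedure requires a dose promptly after D. A dose just after C meets both if C − D is short. The two separate only if C − D is long enough that a dose after C no longer counts as given upon delivery, or if someone injects between D and C. The document gives no value for C − D and describes no delayed clamping. The procedure does not say to inject before clamping. A conflict is possible but not shown.

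**Step 3: could the wording bias the comparison?** Randomization takes place in the preoperative area, before delivery. Obstetricians, anesthesiologists, intraoperative research staff and subjects are blinded. Active and placebo injections come under the same sentence. Whatever moment the anesthesiologist picks, it is picked without knowledge of the arm, so the wording cannot shift timing in one arm relative to the other.

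**Step 4: does timing enter the sample size?** The inputs in Statistical Analysis are difference 0.83, SD 0.83, 1:1 allocation, 20% crossover, power 0.90, two-sided alpha 0.05 and 10% dropout. The stated 33 per group can be reproduced from them:

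- Normal approximation: n = 2 × (1.960 + 1.282)² × (0.83 / 0.83)² = 21.0, rounded up to 22. The t-based calculation gives 23.
- Crossover as a simple divisor: 23 / 0.8 = 28.75, rounded up to 29.
- Dropout: 29 / 0.9 = 32.2, rounded up to 33, or 66 in total.

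None of these inputs is a time or depends on one. Whether a simple divisor is the best allowance for crossover is a separate question and has no bearing here.

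**Step 5: does timing enter the outcome or the analysis?** The primary outcome is the fall in hemoglobin between the preoperative value and the first postoperative day. Nothing in Statistical Analysis conditions on the time of injection. The document offers no basis for expecting the delivery-to-clamping gap to alter a next-day hemoglobin change.

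**The case for a change.** The strongest opposing case is that timing is a core part of an intervention, and a protocol should state it once. The authors named the second twin in both places, so they attended to timing, yet the condition about the cord did not reach the operating instruction. The Background section describes both drugs as acting on smooth muscle, and methylergonovine as also constricting vessels, so a reader may fairly ask whether the cord should be clamped first. Neonatal records are reviewed through 30 days, and interpreting a neonatal event would be easier with a fixed dosing sequence. The carboprost stratum has no administration time of its own. The oxytocin sentence names neither the twin nor the exact event. A clarification would cost one line.

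Part of this stands. The phrases are not identical, and a single wording would be tidier. A report that repeats the research question could describe the dosing more exactly than the procedure guarantees.

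The rest does not carry the point further. The document raises no neonatal exposure concern and gives no clamping practice, so that argument rests on an assumed delay. Extra variability from timing is conceivable but not shown. Applying one instruction to everyone does not mean that every dose is mistimed: on the concern's own logic, only women injected before clamping would be affected. The oxytocin sentence describes routine care common to both arms and is not part of this discrepancy.

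**Conclusion.** This is a difference in precision between a research question and a procedure, which staff and analysts can read together sensibly. Following Study Procedures as written would still give a sound randomized comparison of active drug with placebo on the stated outcome. The wording introduces no bias between arms and leaves alpha, power, the 33 per group and the analysis as they are. Any effect of the gap on the size or variability of the treatment effect cannot be computed, because the document gives no delivery-to-clamping interval.

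The conclusion assumes that clamping follows delivery closely enough for one dose to meet both descriptions. If a site delayed clamping, the two sentences would name different moments and would have to be reconciled. Which event to use would be for the investigators, and this review takes no position on it. Even then the comparison would stay unbiased, because both arms share the instruction and the person giving the dose is blinded. Aligning the phrases is optional editing, and no change to the plan is called for.
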